## **6.2 Analysis Population**

Two analysis populations will be defined:

- FAS: The full analysis data set will contain all subjects, for whom hospital records were pulled and recorded.
- ITT: The intent-to-treat (ITT) population, a subset of the FAS, includes all subjects who satisfied all the inclusion criteria and none of the exclusion criteria. For Stage II of the study, patients who did not receive the MetaNeb® system will be excluded from the ITT population.

The ITT population will be the primary population for the analysis.

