3.4 Study Observations Table

The study observations and documentation timeline is outlined in Table 1.

Table 1. Study Observations Table

Day	Pre-Surgery	Day of Surgery	Post Surgery Day 1 - Day 7	Hospital Discharge	Early Term	Day 30 Post Discharge
Selection Criteria / Enrollment	X					
Informed Consent *	X					
Demographic Data	X					
Medical History	X					
Pre-Surgery Respiratory Status (Patient's Baseline)	X					
Post-Surgical Data (day 0) at day of surgery.		X				
Location (7A & 7P)		X	X			
Respiratory Status (Each Shift)		X	X			
Respiratory Milestones		X	X			
Respiratory Treatments		X	X			
Hospital Discharge Summary				X		
ICU Admission/Discharge Summary (Day 8 - Discharge)				X		
Discharge Respiratory Summary (Day 8 - Discharge)				X		
30-day Readmission					X	
Study Exit Form				X	X	

* Informed consent will be obtained only for subjects in Stage II.

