The secondary endpoints as listed in section 3.3 will be summarized with descriptive summary statistics appropriate for continuous or categorical data, depending on the outcome being summarized:

1. Requirement for invasive mechanical ventilation for more than 48 hours.
2. Requirement for respiratory support for more than 48 hours
3. Length of ICU stay (ILOS)
4. Length of hospital stay (HLOS)
5. Time on mechanical ventilation
6. Readmission to ICU
7. Readmission to hospital

Hill-Rom®	Evaluation of a practice change to include The MetaNeb® System to reduce postoperative pulmonary complications	Page 23 of 31
CBI	8 September 2016	Rev C

Stage I and Stage II results will be compared for the purpose of identifying any statistical associations that can be attributed to use of The MetaNeb® System.

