## 2 STUDY OBJECTIVES AND ENDPOINTS

### 2.1 Primary Objective and Endpoint

The primary objective of Stage I of this study is to estimate the incidence of postoperative pulmonary complications (PPC) in post-surgical patients receiving standard of care per hospital and respiratory care department procedures and policies.

The primary objective of Stage II of this study is to estimate the incidence of PPC in post-surgical patients receiving change in practice therapy regimen, which includes the addition of the MetaNeb® System to the standard of care per hospital and respiratory care department procedures and policies.

The primary endpoint at each stage is to evaluate the proportion of subjects who experience a significant PPC within seven (7) days of: post-surgical hospital admission (Stage I) or post-surgical hospital admission and MetaNeb® System administration (Stage II). A PPC is defined as having one or more of the following:

- 1. Patient requires prolonged mechanical ventilation for > 24 hours**  
Invasive mechanical ventilation (MV) for > 24 hours from post-surgical hospital admission (PSHA)
- 2. Patient requires prolonged respiratory support for > 24 hours from PSHA**

- Requirement for non-invasive ventilation (NI V) or continuous positive airway pressure (CPAP) above patient's baseline requirement, not related to obstructive sleep apnea (OSA), for > 24 hours from PSHA
- Requirement for O2 therapy > 40 % FiO2 or > 5 LPM via NC (and above patient's baseline), for > 24 hours from PSHA

3. **Diagnosis of Pneumonia within 7 days from PSHA**
  - Physician documented pneumonia, and
  - Radiologists report indicating pneumonia / new or expanded infiltrate, and
  - Elevated or low Temperature (> 38° C or < 36° C, or as defined by the site) and/or elevated white count above the upper level of normal as defined by the site
4. **Readmission to ICU (or transfer to an elevated level of care) for pulmonary complications**  
Defined as readmission to the ICU or readmission to an elevated care unit within 7 days from PSHA

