#### **Stage I**

In Stage I of the study, a retrospective review of medical records for post-surgical patients, who received STANDARD THERAPY as defined by current hospital and Respiratory Care department policies and procedures. This will be a retrospective data collection only. Respiratory Care therapies (e.g. nebulizer treatments, chest physiotherapy, etc.) that were

delivered during the first seven (7) days following surgery, including delivered frequency, will be collected.

The purpose of study Stage I is to estimate the incidence of postoperative pulmonary complications in post-surgical patients receiving standard of care per hospital and Respiratory Care department procedures and policies. Data collected in Stage I will include data from the medical records of 200 randomly selected, eligible patients treated during the year prior to the CHANGE IN PRACTICE.

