#### Stage II

In Stage II, a CHANGE IN PRACTICE will be made and patients will receive the routine standard care prescribed by the patient's health care team with the addition of therapy with The MetaNeb® System. With the exception of standard airway clearance and lung expansion procedures, other components of the patients respiratory care regimen will remain the same as during the standard therapy period, however the CHANGE IN PRACTICE will incorporate the use/treatment with The MetaNeb® System as an alternative to usual airway clearance and lung expansion procedures. Use of The MetaNeb® System will follow the labeling of the device. During Stage II, data from approximately 200 patients will be collected from the medical records across the sites. Respiratory Care therapies, including therapy with The MetaNeb® System, that are delivered during the first seven (7) days post-surgery hospital admission in Stage II, including delivered frequency, will be collected.

Exceptions to the above treatment protocols required for patient care as determined by the treating physician will be collected

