### 6.1 Description of Analytical Methods

#### 6.1.1 Derived Variables

**Primary Endpoint:** occurrence of a postoperative pulmonary complication (PPC).

Stage I: during the 7 days post-surgery hospital admission (PSHA)

Stage II: during the 7 days PSHA. Event must occur after MetaNeb® administration.

For each subject, occurrence of a PPC will be set to yes if one or more of the four conditions below occur.

- i. **PPCflg1:** Patient Requires Prolonged Mechanical Ventilation beyond Hour 24 from PSHA.

Duration of invasive mechanical ventilation (IMV) is defined as IMV stop time minus IMV start time where:

IMV Start Time=date & time of the later of start of IMV or PSHA

IMV Stop Time=date & time of the earlier of stop of IMV or PSHA+7

If IMV is required on more than one occasion during the 7 days following PSHA, then the cumulative sum will be calculated.

$$\text{PPCflg1} = \begin{cases} 1 & \text{if the latest IMV stop time is more than 24 hours after PSHA} \\ 0 & \text{otherwise} \end{cases}$$

If IMV start date is available, but the start time is missing, then a clock time consistent with the earliest possible time of the day will be imputed, ex. Hour 00.00 or PSHA clock time.

If the IMV stop date is available, but the stop time is missing, then the IMV stop time will be taken as the assessment time.

- ii. **PPCflg2:** Patient Requires Prolonged Respiratory Support beyond Hour 24 from PSHA

- a) Duration of non-invasive MV (NIMV) is defined as NIMV Stop time minus NIMV start time. NIMV start and stop times are defined similarly to those of IMV.

Imputations for missing NIMV start or stop times will be used similarly to those of IMV.

- b) Duration of CPAP is defined as CPAP Stop time minus CPAP Start time.

- c) Duration of O2 therapy [if >40% FiO2 or >5 LPM via Nasal Cannula] will be calculated similarly.

Duration of respiratory support is defined as the sum of durations of NIMV, CPAP, and O2 therapy during the 7 days following hospital admission.

$$\text{PPCflg2} = \begin{cases} 1 & \text{if the latest NIMV, CPAP, or O2 therapy stop time} \\ & \text{is more than 24 hours after PSHA} \\ 0 & \text{otherwise} \end{cases}$$

- iii. **PPCflg3:** Diagnosis of pneumonia

- iv. **PPCflg4:** Readmission to ICU (or transfer to an elevated care) for PPC with 7 days of PSHA

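### The primary ITT set drops Stage II patients who did not receive MetaNeb but filters Stage I on eligibility only, which opens the between-stage comparison to selection bias of unknown size and direction

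*SAP*

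**What the plan says.** SAP 6.2 defines two sets. The FAS holds every subject whose hospital records were pulled. The ITT set is the part of the FAS that meets all inclusion and no exclusion criteria, with one further condition: "For Stage II of the study, patients who did not receive the MetaNeb® system will be excluded from the ITT population". The section then says "The ITT population will be the primary population for the analysis".

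No matching condition applies to Stage I, which SAP 3 describes as "200 randomly selected, eligible patients treated during the year prior to the CHANGE IN PRACTICE". The documents do speak of Stage I patients as having received standard therapy. The Protocol Synopsis (Treatment of Subjects), however, defines that as whatever respiratory care was ordered or delivered in routine practice, so the phrase removes almost nobody.

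A second rule applies to Stage II only. SAP 6.1.1 says of the primary endpoint: "Event must occur after MetaNeb® administration". SAP 2.1 carries matching wording.

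On the purpose of the data, Protocol 3.5.2 says "Stage I and Stage II results will be compared for the purpose of identifying any statistical associations" that can be attributed to the device.

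**The concern.** Receipt of MetaNeb is a post-baseline event. The observation tables in both documents place selection and consent before surgery, and consent applies to Stage II only ("Informed consent will be obtained only for subjects in Stage II"). The device is used afterwards. Between those points a patient may go untreated for reasons tied to prognosis, and the plan expects departures: "Exceptions to the above treatment protocols required for patient care as determined by the treating physician will be collected".

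If the untreated are mainly patients who were too ill or who deteriorated early, removing them makes Stage II look better with no device effect. If they are mainly patients who were well or left early, removing them makes Stage II look worse. If receipt is unrelated to risk, there is no bias. Stage I keeps all such patients in every case.

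The set is labelled ITT but is as-treated in one stage, so a reader would assume a protection that it lacks. Without randomisation, like-for-like selection of patients is one of the few safeguards this design has. Patients who decline consent are never enrolled and are not part of this point.

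**Working it through.** **Can the plan detect or repair the problem?** SAP 6.1.2 counts enrolled subjects by site and overall, with no count of non-recipients and no reasons. The FAS has no eligibility condition, and SAP 6.3 assigns it no analysis. The safety population in SAP 6.4.1 also requires receipt. No analysis of all eligible patients is planned. Treatment exceptions are collected, but no rule says how they are used.

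**Inputs from the documents.** About 200 patients per stage (Protocol Synopsis); true rate p of 5-15% (Protocol 3.5.1); two-sided 5% tests (SAP 6). The plan has no figure of its own to reproduce, because SAP 5 says that no formal sample size determination was made.

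**Assumptions.** No device effect; the same p among all eligible patients in both stages; an untreated share q of Stage II; untreated patients at RR times the risk r of treated patients; a pooled two-proportion z-test, since the SAP names none. Events lost through the Stage II timing rule in treated patients are ignored.

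**Formula.** From p = (1 − q)r + q·RR·r, the rate in the Stage II ITT set is

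r = p / (1 − q + q·RR),

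and the relative reduction is q(RR − 1) / (1 + q(RR − 1)), whatever the value of p.

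| q | RR | Relative shift in Stage II | Stage II rate if p = 15% |
|---|---|---|---|
| 5% | 2 | 0.05/1.05 = 4.8% lower | 14.3% |
| 5% | 3 | 0.10/1.10 = 9.1% lower | 13.6% |
| 10% | 2 | 0.10/1.10 = 9.1% lower | 13.6% |
| 10% | 3 | 0.20/1.20 = 16.7% lower | 12.5% |
| 15% | 2 | 0.15/1.15 = 13.0% lower | 13.0% |
| 15% | 3 | 0.30/1.30 = 23.1% lower | 11.5% |
| 5% | 0.5 | 1/0.975 − 1 = 2.6% higher | 15.4% |
| 15% | 0.5 | 1/0.925 − 1 = 8.1% higher | 16.2% |
| any | 1 | none | 15.0% |

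**Chance of a false significant result.** This comes from exact binomial enumeration of the z-test, with 200 patients in Stage I and 200(1 − q) in Stage II. With no bias and 200 per stage, it is 2.4-2.5% on each side.

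- q = 5-15%, RR = 2-3, false benefit: 3.1-6.9% at p = 5%, 3.6-11.4% at p = 10%, 4.0-15.6% at p = 15%.
- q = 2%, RR = 2-3, p = 5-15%, false benefit: 2.8-3.6%.
- q = 5-15%, RR = 0.5, p = 5-15%, false harm: 2.7-5.4%.

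**Why restoring the denominator alone would not do.** If untreated patients return to the set but the SAP 6.1.1 timing rule stays, they can never have a counted event. The Stage II rate becomes (1 − q)r on 200 patients. With p = 15%, q = 10% and RR = 3 it is 0.9 × 12.5% = 11.25%, further from the true 15% than the present 12.5%. Over q = 5-15% and RR = 2-3 the spurious reduction is 9.5% (1 − 0.95/1.05) to 34.6% (1 − 0.85/1.30), with false benefit of 4.0-34.9%. Even at RR = 1 the reduction equals q, so 5-15%.

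**The case against.** The strongest reply is that the importance of the asymmetry is unproven. Nothing in the documents suggests that 5-15% of consented, eligible patients would go untreated, and the 15.6% figure is a single corner (15% rate, 15% untreated, three times the risk). At 5% untreated and twice the risk, the shift is only 0.24-0.71 percentage points over a 5-15% rate, and false benefit is 3.1-4.0%. This stands as a limit on the size claimed. It does not remove the asymmetry, which is certain from the text.

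Second, SAP 6.3 plans only per-stage proportions with confidence intervals, so the error rates belong to a test that the SAP does not contain. That is correct. But the protocol commits to a comparison, and the shift in the Stage II rate is the same whether the rates are tested or read side by side.

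Third, SAP 2.1 and Protocol 3.3 refer to patients receiving the regimen or treated with the device, so a receivers-only set fits one stated target. The documents are mixed here, since Protocol 3.1.1 describes a facility-level practice change. For a description of Stage II alone, the set is coherent and only its label is wrong. For the comparison, a treated-only target would need a Stage I group selected in a comparable way, and none is defined.

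Fourth, the FAS and the exception records keep some of the information. They do, but no analysis or accounting uses it.

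**Conclusion.** The concern holds. The primary set is filtered on treatment receipt in one stage and not in the other, and nothing elsewhere in the plan corrects this. Size and direction cannot be determined from the documents. Under the assumed 5-15% untreated at 2-3 times the risk, the spurious reduction is 4.8-23.1%. At 2% untreated the effect is small, at half the risk it reverses, and it vanishes if receipt is unrelated to risk. These ranges rest on the assumed untreated share, risk ratio and test; only the 5-15% rate, the 200 per stage and the 5% level come from the documents. Because the rule governs the primary population, and the outcomes of untreated patients may not be abstracted under it, it should be changed before Stage II is analysed.

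**What to change.** 1. In SAP 6.2, define the primary set in both stages as all patients sampled (Stage I) or enrolled (Stage II) who meet the eligibility criteria as assessed at post-surgical admission, regardless of MetaNeb receipt or later exit. Apply the exclusion criteria to Stage I charts in the same way.
2. In the same revision, delete the rule in SAP 6.1.1 that Stage II events must follow MetaNeb administration, and the matching wording in SAP 2.1, so that events count from post-surgical hospital admission in both stages. Step 1 should not be made without this.
3. Report the number of Stage II non-recipients by site, with reasons.
4. Keep the eligible receivers-only set as a sensitivity analysis, labelled as-treated. It is not the safety population, which has no eligibility condition.
5. Reconcile the exit wording in Protocol 3.2.2 with the new set, stating that outcome data to day 7 are still abstracted after exit.

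The cost is wording in SAP 2.1, 6.1.1 and 6.2, a minor protocol alignment, and chart abstraction to day 7 for untreated or exited patients. No new enrolment is needed. The drawback is that non-receipt somewhat dilutes the estimated effect.

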### **6.3 Analysis Methods – Primary and Secondary Endpoints**

#### **Primary Endpoint— Proportion of subjects who have a postoperative pulmonary complication**

The proportion of subjects who have a PPC within 7 days of post-surgery hospital admission will be presented with 95% confidence intervals.

Incidence of each of the 4 components that contribute to the primary endpoints, will also be presented.

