Number of Subjects:	The sample size will be approximately 400 patients, 200 in the retrospective STANDARD THERAPY group and 200 in the prospective CHANGE IN PRACTICE group.		
Study Population:	The study population consists of adult post-surgical patients who have undergone thoracic, aortic or upper abdominal surgery who are at high risk for PPCs.		
Inclusion/Exclusion Criteria:	
Inclusion Criteria:
 
Patients who meet all of the following criteria will be included in the study:
 
• Age \geq 18 years• Post-thoracic, -upper abdominal or -aortic surgery• Open surgical procedure• Incision at or above the umbilicus• High risk defined by:
• Documented ASA class \geq 3 
OR
 
• Documented ASA class 2 AND One or more of the following:
• Current smoker or smoking history within past 6 months• History of COPD• Documented obesity and/or BMI \geq 30 kg/m²• Age \geq 75 
Exclusion Criteria:
 
Patients who meet any of the following criteria will be excluded (or will be exited) from the study:
 
• Contraindication to Continuous High Frequency Oscillation (CHFO) therapy (e.g. untreated tension pneumothorax)• Minimally invasive, or “... scopic” procedure.• Spinal surgery involving a posterior approach• Surgery for organ transplant• Chronic invasive positive pressure ventilation (PPV)		

Statistical Methods:	
Descriptive summary statistics will be provided for demographics, the primary and secondary endpoints. Continuous data will be summarized with N, mean, median, standard deviation, min, and max. Categorical data will be summarized with the number and percent of patients in each category. Time to event data (ex. Time to readmission) will be summarized with methods appropriate for survival data including a Kaplan-Meier plot.
 
Ninety-five percent (95%) confidence interval will be computed for the primary endpoint, the incidence of significant postoperative pulmonary complications. Incidence rates for various demographic subsets, surgery types, and different population subsets may be presented as outlined in the statistical analysis plan document, to be published prior to study completion. Stage I and Stage II incident rates will be compared for the purpose of identifying any statistical associations that can be attributed to use of The MetaNeb® System.
		

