3.3 Evaluation Criteria/Effectiveness

The CHANGE IN PRACTICE therapy regimen (which includes therapy with The MetaNeb® System) will be evaluated to determine if there is a decrease in the number of patients who experience Significant Postoperative Pulmonary Complications among the group of patients treated with The MetaNeb® System. Endpoints are described below:

Primary Endpoint:

Significant Postoperative Pulmonary Complication (PPC):

One or more of the following that occurs within seven (7) days of the post-surgical admission will be considered a Significant Postoperative Pulmonary Complication (PPC)

- **Patient Requires Prolonged Mechanical Ventilation:**

Defined as patient requirement for invasive mechanical ventilation (MV) for > 24 hours (after hour 24) post-operatively. This includes patients that require re-intubation and MV after hour 24, regardless of length of time on MV in the first 24 hours postoperatively.

Hill-Rom®	Evaluation of a practice change to include The MetaNeb® System to reduce postoperative pulmonary complications	Page 17 of 31
CBI	8 September 2016	Rev C Protocol #: CR-RR2015-001

- **Patient requires prolonged respiratory support for > 24 hours from post-surgical admission**
 - Requirement for non-invasive ventilation (NIV) above patient's baseline requirement after hour 24, or continuous positive airway pressure (CPAP) above patient's baseline requirement after hour 24.
 - Requirement for O₂ therapy > 40 % FiO₂ or > 5 LPM via NC (and above patient's baseline) after hour 24 postoperatively.
- **Diagnosis of Pneumonia Within Seven (7) Days**
 - Physician documented pneumonia AND
 - Radiologists report indicating pneumonia / new or expanded infiltrate AND
 - Elevated or low Temperature (> 38° C or < 36° C, or as defined by the site) and/or elevated white count above the upper level of normal as defined by the site
- **Readmission to ICU (or transfer to an elevated level of care) for pulmonary complications within seven (7) days of the post-surgical hospital admission**

Defined as readmission to the ICU within seven days of post-surgical hospital admission or readmission to an elevated care unit such as special care or ICU step-down unit after being moved to a lower (e.g. general care) floor (e.g. patient discharged from ICU on day 4 at 0800 is readmitted to the ICU before day 8 at 0800).

Secondary Endpoints:

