3.4.1 Study Observations Table Detailed Description

Hill-Rom®	Evaluation of a practice change to include The MetaNeb® System to reduce postoperative pulmonary complications			Page 20 of 31
	CBI	8 September 2016	Rev C	Protocol #: CR-RR2015- 001

Documentation of observations will be completed by study staff based on review of the patient's medical records. A detailed description of documentation requirements for each parameter is below.

Demographic Data: The following data will be recorded from the patient medical record: Age, Height, Weight, Race, Gender, ASA score, Documented obesity and/or $BMI \geq 30 \text{ kg m}^2$.

Medical History: Pulmonary history will be recorded from the patient medical record including: Asthma, Cystic Fibrosis, Bronchiectasis, COPD, Neuromuscular Disease, Other Pulmonary Condition(s), Obstructive Sleep Apnea

Pre-surgery Respiratory Status: Pre-surgery respiratory status such as Invasive Mechanical Ventilation, Non-invasive Mechanical Ventilation, CPAP, Supplemental oxygen will be recorded.

Post-Surgery Data (day 0): Following surgery, the albumin level (if available in the medical record) and surgery type will be recorded.

Location: The post-surgery location of each patient upon return to the hospital unit or floor (ICU, General Care, etc.) will be recorded. The patient's location during the first seven days, or until the time of discharge from the hospital, whichever occurs first, will also be recorded at regular intervals based on entries in the medical record.

Respiratory Status: The respiratory status of each patient, following surgery will be recorded. Respiratory status during the first seven days, or until the time of discharge from the hospital, whichever occurs first, will also be recorded at regular intervals based on entries in the medical record. Respiratory status will include documentation of the mode of support, the device in use and the settings.

Respiratory Milestones: Key respiratory milestones that occur each day will be recorded based on entries in the medical record. These include 1) extubation, 2) re-intubation, 3) return to baseline respiratory support, 4) Diagnosis of Pneumonia and 5) Readmission to the ICU or an elevated level of care. These milestones will be recorded for each day until discharge from the hospital, or through day seven (7) following the day of surgery, whichever occurs first.

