3.5 Statistical Methods and Analysis

3.5.1 Sample Size Estimation:

This study is designed to provide information on the benefits of the addition of the MetaNeb® System in reducing the incidence of postoperative pulmonary complications (PPCs) in high-risk subjects undergoing high-risk surgical procedures (upper abdominal, thoracic, aortic). The study will be conducted in 2 stages:

- Stage I: To update/confirm the estimate of the current incidence of PPC's with current Standard of Care Practice. Recent published articles suggest incidence rates between 5%-15%, depending on the patient population and type of surgery. This stage of the study will be a retrospective pre-intervention observational period, conducted at 2 - 4 hospitals/sites, with no intervention in the patients' post-surgical

Hill-Rom®	Evaluation of a practice change to include The MetaNeb® System to reduce postoperative pulmonary complications			Page 22 of 31
	CBI	8 September 2016	Rev C	Protocol #: CR-RR2015- 001

management. Data from approximately 200 subjects will be collected. The incidence rate will be calculated, along with a 95% confidence interval.

- Stage II: To assess the impact of the MetaNeb® System on the incidence of PPC's. This stage of the study will be a prospective post-intervention period conducted in the same 2 - 4 hospital sites with an intervention involving use of the MetaNeb® System in addition to Standard of Care Practice.

3.5.2 Statistical Analysis:

- Summary statistics and data listings will be provided.
- Demographic data will be summarized. For continuous type data (e. g. Age), descriptive summary statistics (N, mean, median, standard deviation, min, and max) will be presented. For categorical variables (gender, race, etc.) the number and percent of patients in each category will be provided.

Primary Endpoints:

The incidence of significant postoperative pulmonary complications (as defined in section 3.3) along with 95% confidence interval will be generated. Additionally, the incidence rates will be summarized for various demographic subsets, by surgery type, and for different population subsets. The descriptive summary statistics for the subsets may be presented side-by-side for ease of comparison. The specific subsets to be summarized will be described in a separate document (the statistical analysis plan).

Secondary Endpoints:

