## 1 Introduction

The study will be conducted in two stages.

Stage I of the study, STANDARD THERAPY, is a retrospective review of medical records for 200 randomly selected post-surgical patients, who received standard of care therapy as defined by current hospital and respiratory care department policies and procedures. Data collected in Stage I will include data from the medical records of eligible patients treated during the year prior to the start of Stage II. This allows for inclusion of patients from the seasonally consistent time period as well as those from most recent time period, during which care practices are most similar between the 2 stages.

Stage II of the study, a CHANGE IN PRACTICE will be made and patients will receive standard care with the addition of therapy with The MetaNeb® System. Other standard airway clearance and lung expansion therapies typically delivered by Respiratory Therapy will not be delivered during Stage II. Data from approximately 200 patients will be collected from the medical records at 3 sites. However, an adjustment in sample size may be made based on the incidence rate for post-operative pulmonary complications in Stage I, to allow for a robust estimate and assessment of the effect of therapy with The MetaNeb® System.

Stage II will start after gathering and analysis of data from Stage I

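### SAP 6.3 specifies no between-stage estimate or test, although the protocol says the stages will be compared and the SAP's own stated purpose is to evaluate the device's effect

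*SAP*

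**What the plan says.** **The comparison.** Protocol 3.3 states that the new regimen "will be evaluated to determine if there is a decrease in the number of patients who experience Significant Postoperative Pulmonary Complications". The synopsis adds: "Stage I and Stage II incident rates will be compared for the purpose of identifying any statistical associations". Protocol 3.5.2, after listing the secondary endpoints, says: "Stage I and Stage II results will be compared for the purpose of identifying any statistical associations". SAP 3 repeats the effect-evaluation purpose. SAP 1 allows the sample size to change after Stage I "to allow for a robust estimate and assessment of the effect of therapy with The MetaNeb® System".

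**The planned analysis.** SAP 2.1 gives each stage its own objective, an incidence estimate. SAP 6.3 says of the primary endpoint: "The proportion of subjects who have a PPC within 7 days of post-surgery hospital admission will be presented with 95% confidence intervals". The four components are also tabulated. Binary secondary endpoints get proportions; durations get mean, median and SD. SAP 6 sets a two-sided 5% level for all statistical tests.

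**Case mix.** Protocol 3.5.1 cites PPC rates of 5% to 15%, varying with population and type of surgery. Protocol 3.4.1 says: "Following surgery, the albumin level (if available in the medical record) and surgery type will be recorded". SAP 6.1.2 reports enrolment by site.

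**Two lesser items.** On incidence by subset, Protocol 3.5.2 says: "The specific subsets to be summarized will be described in a separate document (the statistical analysis plan"). On readmission, the synopsis says: "Time to event data (ex. Time to readmission) will be summarized with methods appropriate for survival data including a Kaplan-Meier plot".

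**The concern.** A trial whose stated question is comparative needs a planned comparative estimate. Followed to the letter, this SAP ends with two separate incidence tables. Someone must then decide whether to report a difference or a ratio, which interval and test to use, and whether to adjust and for what.

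Timing sharpens this. SAP 1 has Stage I gathered and analysed before Stage II starts, so half of the comparison is known early. Fixing the contrast before Stage II outcomes are seen is the safeguard that remains.

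The design adds a second reason. In a non-randomised before-and-after study at several sites, a crude difference carries any change in the kind of patient treated. SAP 6.1.3 to 6.1.6 would show shifts in age, ASA score or COPD, but no SAP table shows surgery type, so a shift there would go unseen.

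**Working it through.** The plan states no effect size, power or derived sample size (SAP 5), so there is no figure to reproduce. The main check is textual.

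**1. Promise against specification**

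| Item | Stated aim | What the SAP specifies |
|---|---|---|
| PPC incidence | Compared between stages (synopsis, Protocol 3.5.2); look for a decrease (Protocol 3.3) | Proportion with 95% CI (6.3) |
| Secondary endpoints | Compared between stages (Protocol 3.5.2) | Proportions, or mean, median and SD (6.3) |
| Stage II objective | Effect of the device (SAP 3) | Incidence in Stage II (2.1) |
| Significance level | Two-sided 5% (SAP 6) | No test defined |

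No other SAP section supplies a contrast.

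**2. What the missing contrast would look like**

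Inputs: n = 200 per stage (synopsis); Stage I rates of 5%, 10% and 15% (Protocol 3.5.1). A halving in Stage II is assumed. Half-width = 1.96 × √(p₁q₁/200 + p₂q₂/200).

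- 5% to 2.5%: 1.96 × √((0.0475 + 0.024375)/200) = 3.7 points, for a 2.5-point reduction.
- 10% to 5%: 1.96 × √((0.09 + 0.0475)/200) = 5.1 points, for a 5.0-point reduction. The Newcombe interval is −0.2 to 10.4.
- 15% to 7.5%: 1.96 × √((0.1275 + 0.069375)/200) = 6.2 points, for a 7.5-point reduction.

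In the middle case the lower limit lies almost at zero, so the choice of interval or adjustment could change the reading.

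**3. Separate intervals are not a substitute**

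For 10% against 5%, the Clopper-Pearson intervals are 6.2% to 15.0% and 2.4% to 9.0%, which overlap. The exact binomial chance that two such intervals separate in the device's favour is 14%.

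A direct two-proportion test has power Φ[(0.05 − 1.96√(2 × 0.075 × 0.925/200)) / √(0.1375/200)] = Φ[(0.05 − 0.0516)/0.0262] = 48%.

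**4. Case mix, as illustration only**

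Assume no device effect, three equally common surgery types, and risks of 15%, 10% and 5%. The crude rate is (15 + 10 + 5)/3 = 10%. Moving 10 points of the mix from the highest- to the lowest-risk type changes it by 0.10 × (5 − 15) = −1 point, or 2 patients per 200. Enumerating all outcomes of a two-sided pooled z test at 200 per stage gives rejection rates of 4.8% (10% v 10%), 6.1% (10% v 9%) and, for a 20-point stress case, 10.4% (10% v 8%).

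Simulation (40,000 runs per scenario; three sites; surgery mix 50/10/40% with risks 15/10/5%; shifts of 0, 10 and 20 points) gave rejection of 4.9%, 5.1% and 5.0% for a Mantel-Haenszel risk difference stratified by site and surgery type. The crude test gave 4.7%, 5.9% and 10.2%. The largest half-width cost in any scenario was 5.73 − 5.60 = 0.13 points.

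**5. The estimand has to be named**

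Take the 50/10/40% mix, the 20-point shift (Stage II mix 30/10/60%), and risk halved in every type, so reductions are 7.5, 5 and 2.5 points.

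- Stage I mix: 0.5 × 7.5 + 0.1 × 5 + 0.4 × 2.5 = 5.25 points.
- Stage II mix: 0.3 × 7.5 + 0.1 × 5 + 0.6 × 2.5 = 4.25 points.
- Mantel-Haenszel weights, proportional to ab/(a + b) for Stage I and II shares a and b, are 0.1875, 0.05 and 0.24. The result is (1.406 + 0.25 + 0.6)/0.4775 = 4.7 points.

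The same data thus support three defensible answers.

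**The case against.** **Two proportions with intervals already let a reader form a difference.** True. It would be wrong to infer that no effect could ever be computed. What is missing is its specification. The protocol also promises a comparison without naming an estimate, so the SAP was the place to settle it.

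**The study may be meant as descriptive.** SAP 2.1 and the absence of a formal sample size fit that reading. Protocol 3.3, 3.5.2 and the synopsis, and SAP 3, do not. The SAP carries a date of 16 August 2016 and Protocol Rev C one of 8 September 2016, so they may simply not have been aligned. Either way the documents need reconciling.

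**Leaving out adjustment contradicts nothing.** Correct: neither document promises adjustment. That part is a recommendation drawn from the design.

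**The case-mix figures do not measure the omission.** Agreed. The risks by surgery type and the shifts are assumed. The simulation has no site effect and equal site shares in both stages, so it says nothing about site mix. Its only confounder is also its stratifier, so good performance is partly built in.

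**A reader might infer that the SAP also breaks firm promises on subsets and Kaplan-Meier curves.** The text is weaker than that. The synopsis makes subset summaries optional, whereas Protocol 3.5.2 commits to them and leaves the list to the SAP, which has none. The Kaplan-Meier summary appears only in the synopsis. Protocol 3.5.2 treats readmission with ordinary descriptive statistics, as SAP 6.3 does. Both are alignment notes.

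**Conclusion.** The point holds on the text alone: the study's own comparative question has no prespecified estimate, interval, test or model. It should be settled before Stage II outcomes are seen, because the protection of prespecification is lost afterwards.

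The half-widths of 3.7 to 6.2 points assume 200 per stage and a halved Stage II rate; they show how much could turn on an unplanned choice. The documents do not support reading the false-positive rates of 6.1% or 10.4% as the error rate of this trial, or treating the lack of adjustment as a breach of the protocol.

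**What to change.** Before Stage II outcomes are seen, amend SAP 6.3 as follows.

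- **Primary comparison:** Stage II minus Stage I PPC risk difference, 95% CI and two-sided 5% test, stratified by site and surgery type (thoracic, aortic, upper abdominal). Mantel-Haenszel is one suitable method, with a sparse-stratum rule fixed in advance.
- **Estimand:** state whether it is the Mantel-Haenszel-weighted difference or one standardised to a named stage's case mix. Report the crude difference alongside.
- **Secondary endpoints:** the same contrast for binary endpoints; mean differences with CIs for durations.
- **Tables:** surgery type by stage, and PPC by stage within surgery type.
- **Wording:** align the Stage II objective in SAP 2.1 with the comparison, and phrase the conclusion as an association.
- **Alignment:** list the subsets in the SAP or withdraw the commitment in Protocol 3.5.2. Add the time-to-readmission method to the SAP or remove it from the synopsis.

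If description is all that is intended, amend the synopsis, Protocol 3.3 and 3.5.2, and SAP 3 to say so.

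The cost is text and programming: surgery type is already recorded and site is already reported. The adjusted interval may be slightly wider, by about 0.1 points in the illustrative runs. Adjustment does not remove secular trend or unmeasured confounding. Nor does it repair the rules that apply to Stage II only, namely counting events only after device administration (SAP 6.1.1) and excluding patients who did not receive the device (SAP 6.2). Those need separate reconciliation.
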